#### Efficacy:

- To evaluate the effect of aripiprazole once monthly on:
  - o 30-, 90-, and 180-day rates of unscheduled psychiatric ED visits compared with prior 30-, 90-, and 180-day unscheduled visits
  - Psychiatric ED visits plus hospitalizations compared with prior 30-, 90-, and 180-day psychiatric visits plus hospitalizations
  - o Total psychiatric hospitalization days over the 180-day study period compared with the total psychiatric hospitalization days over the prior 180-day period
  - o Change from baseline in CGI-S and CGI-I scores at 30-, 90-, and 180-days
- To evaluate changes from baseline for the following indicators for CMR:
  - Weight and BMI
  - Fasting glucose concentrations
  - HbA1c concentrations
  - o Fasting plasma lipid concentrations (i.e., fasting triglyceride [primary analysis], total cholesterol, high-density lipoprotein [HDL], and low-density lipoprotein [LDL])

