# 9.1.2 Screening Period

All recruitment methods conformed to the guidelines of the IRB at the clinical site. The subjects participating in this study had to be capable of understanding the nature of the study. The ICF contained a full description of the procedures and their associated risks. Subjects were given both verbal and written descriptions of the procedures, discomforts, risks, and potential benefits by study personnel. After briefing subjects on the reasons for the research, their rights as a subject, and the risks involved, they were given the opportunity to ask questions. Subjects were asked to paraphrase the ICF. When ready, subjects were asked to give written consent to participate in the study. After the ICF was signed by both the subject and the investigator, each subject was given a copy of the signed ICF. The investigator had full responsibility for all issues pertaining to assent and informed consent. Procedures to be followed when obtaining informed consent are detailed in Section 5.1.

During the Screening Period, subjects could be treated with any oral antipsychotic medication of the clinician's choice, with the exception of clozapine. However, oral olanzapine was permitted during the Screening Period only for subjects who were eligible for Phase A.

Eligibility for the study was determined during the screening period, which could occur at any time, beginning with the first day of hospitalization. Eligibility for the study was assessed via the following:

- Confirmation of a current diagnosis of schizophrenia according to Diagnostic and Statistical Manual, Fifth Edition (DSM-5) criteria
- Review of inclusion and exclusion criteria
- Complete medical history, including demographics, complete psychiatric history including all psychiatric and non-psychiatric hospitalizations and medical interventions occurring within the 6 months prior to the date of signing the ICF:
  - O Data regarding psychiatric and non-psychiatric hospitalizations, including treatment records relevant to determination of study eligibility and identified outcome variables related to ED, outpatient and inpatient treatment episodes as described in the inclusion and exclusion criteria (Section 9.3.1 and Section 9.3.2, respectively) occurring within the 6 months prior to the date of signing the ICF were obtained by searching MO

Final; 26 Feb 2018 Page 25 of 80

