## 9.1.4 Phase B (Treatment Phase)

#### **9.1.4.1** Baseline

Baseline was considered Day 1, or first day of long-acting injectable treatment, of Phase B. However, some subjects could have had their baseline assessments (including any remaining clinical laboratory tests required for screening) performed any time during or immediately after treatment with oral antipsychotic aripiprazole (unless eligible to skip Phase A in which it is any oral antipsychotic), ideally prior to starting long-acting injectable aripiprazole. Participants were allowed, with Principal Investigator approval, to enter the study after starting treatment with long-acting injectable aripiprazole in the hospital and baseline assessments were performed as soon as feasible within 48 hours of hospital discharge.

Final; 26 Feb 2018 Page 27 of 80

Subjects who completed the baseline assessments and met the criteria for inclusion and not for exclusion (Section 9.3.1 and Section 9.3.2) began the Treatment Phase (Phase B).

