#### 9.1.4.2 Treatment Phase

Eligible subjects who had a history of tolerating oral aripiprazole or were currently taking oral aripiprazole entered Phase B directly from the Screening Period. All other subjects entered Phase B following successful completion of Phase A. After the baseline assessments were completed, the subject received the first aripiprazole once monthly IM injection, in conjunction with the first of 14 doses of concomitant oral antipsychotic medication (see Figure 1). Use of concomitant oral aripiprazole during this lead-in was per the investigator's judgment based on the prescribing instructions.

All subjects must have attended scheduled visits at the Baseline Visit and Weeks 2, 4, 8, 12, 16, 20, and 24, totaling 180 days. Aripiprazole once monthly injections occurred at the Baseline Visit and every 28 (-2, +5) days at Weeks 4, 8, 12, 16, 20, and 24, totaling seven injections. After the

Final; 26 Feb 2018 Page 28 of 80

initial injection of 400 mg, the monthly dosage could be decreased to 300 mg, based on the clinical judgment of the investigator. All aripiprazole once monthly injections were administered based on the investigator's judgment and the prescribing information. For subjects who entered the studies after starting the first dose of long-acting injectable aripiprazole in the hospital, if the initial injection was not 400 mg, the second injection should have been 400 mg, and thereafter, the monthly dose could be decreased to 300 mg, based on clinical judgment of the investigator.

For subjects who were psychiatrically stabilized and discharged prior to the completion of the required 14-day course of oral antipsychotic medication, a pre-discharge assignment was given to a CSW/SC. The CSW/SC maintained regular contact with the subject until the first outpatient visit in Phase B (Week 2), when oral aripiprazole was discontinued. Regular contact was defined as no less than weekly, but could have been more frequent depending on the clinical judgment of the CSW/SC and outpatient treatment team. Following the Week 2 Visit, subjects were to have contact with their assigned CSW/SC based on routine clinical care. Contact with the CSW/SC could be in person or by telephone, as clinically appropriate.

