## 9.1.4.3 Early Termination

All subjects who completed or withdrew from the study received a telephone call for safety follow-up at 30 ( $\pm$  5) days after the last study visit unless they withdrew their consent for participation in the study. This telephone contact was made to assess if there were any AEs experienced since the last visit. In addition, the subject was asked about any new medications or changes in existing medications and the information was documented in the source documentation. The study site registered the contact in the interactive voice response system or interactive web response system.

The end of the study was the date of the last study visit for the last subject.

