#### 9.5.2 Schedule of Assessments

The Schedule of Assessments for the study is provided in Table 3.

Final; 26 Feb 2018 Page 46 of 80

**Table 3:** Schedule of Assessments

Visit			1	2	3	4	5	6	7	8 q
Study Period	Screening/ Assessment	Phase A (Oral Tolerability Phase a )	Phase B (Treatment Phase)							
Day	Variable	-3 to -1	Baseline Day 1 b,g	15 g	30	60	90	120	150	180
Week				2 e	4	8	12	16	20	24
Procedure										
Informed consent	X									
Confirmation of diagnosis of schizophrenia (DSM-5)	X									
Review inclusion/and exclusion criteria	X									
Demographic information	X									
Complete medical history	X									
Complete psychiatric history c	X									
Antipsychotic therapy – current use and history d	X									
Electrocardiogram	X									
Urine pregnancy test e	X									X
Documentation of psychiatric and non-psychiatric hospitalizations and interventions f	X									
Contact from the CSW/SC via telephone or in-person g			Xg	Xg						
Clinical interview and mental status examination h					X	X	X	X	X	X
Vital signs i	X		X	X	X	X	X	X	X	X
Height, weight, BMI j	X		X	X	X	X	X	X	X	X
Screening or safety clinical laboratory testing as needed k,l,m	Xm		Xr	Xr	Xr	Xr	Xr	Xr	Xr	Xr
Fasting lipid profile n	X		X		X		X			X
HbA1c 	X		X		X		X			X
Prolactin k			X		X					X
CGI-I			X	X	X	X	X	X	X	X

Final; 26 Feb 2018 Page 47 of 80

**Table 3:** Schedule of Assessments

Visit			1	2	3	4	5	6	7	8 q
Study Period	Screening/ Assessment	Phase A (Oral Tolerability Phase a )	Phase B (Treatment Phase)							
Day	Variable	-3 to -1	Baseline Day 1 b,g	15 g	30	60	90	120	150	180
Week				2 e	4	8	12	16	20	24
Procedure										
CGI-S	X									
AIMS, BARS, SAS	X		X	X	X	X	X	X	X	X
PSP			X							X
C-SSRS o	X		X	X	X	X	X	X	X	X
Oral aripiprazole treatment a,p		X	X							
Administer aripiprazole once monthly			X		X	X	X	X	X	X
Injection site assessment			X		X	X	X	X	X	X
Reporting of AEs	X	X	X	X	X	X	X	X	X	X
Concomitant medications	X	X	X	X	X	X	X	X	X	X

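### The Week 24 schedule spans 168 days, not 180, and the plan does not secure ascertainment to the end of the 180-day post-discharge window

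*Combined protocol and SAP*

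**What the plan says.** Section 9.1.4.2 (repeated in the synopsis) has subjects attend "scheduled visits at the Baseline Visit and Weeks 2, 4, 8, 12, 16, 20, and 24, totaling 180 days". Injections are given at baseline and "every 28 (-2, +5) days at Weeks 4, 8, 12, 16, 20, and 24, totaling seven injections". In Table 3 the day row for Weeks 4, 8, 12, 16, 20 and 24 reads "30 60 90 120 150 180", so one visit carries both the Week 24 and the Day 180 label. On the time origin, section 9.1.4.1 states "Baseline was considered Day 1, or first day of long-acting injectable treatment, of Phase B".

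The endpoints use calendar windows. Section 9.7.1.1 counts 30, 90 and 180 days after hospital discharge, and section 8.2 includes "Total psychiatric hospitalization days over the 180-day study period compared with the total psychiatric hospitalization days over the prior 180-day period". A footnote to Table 3 allows discharge at any time after the first injection.

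On ascertainment, section 9.1.2 limits the MO HealthNet (Medicaid) and DMH search to events "occurring within the 6 months prior to the date of signing the ICF", and Table 3 marks documentation of hospitalizations at screening only. Section 9.1.4.2 has all episodes of care recorded in source documents, without a cut-off. After the last visit, section 9.1.4.3 says that subjects "received a telephone call for safety follow-up at 30" (± 5) days, to ask about AEs and medication changes.

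**The concern.** The design compares each subject with himself or herself over windows meant to be equal in length. The stated 180-day visit schedule is what would make the prospective window match the retrospective one. If the schedule is in fact 168 days, and is counted from an earlier origin than the endpoint, the last scheduled contact falls before the 180-day window closes. Events in the uncovered days would go uncounted on the once-monthly side only, which would lower the apparent post-switch 180-day rates of hospitalization and ED visits and the total of hospital days.

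A visit date does not by itself end ascertainment. The question is therefore whether the plan names anything else that carries event capture to the end of the window.

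**Working it through.** **1. The stated total.** From the listed weeks, 24 × 7 = 168 elapsed days. From the injections, six intervals after baseline give 6 × 28 = 168. With baseline as Day 1, that is study Day 169. The stated 180 is not reproduced; the gap is 180 − 168 = 12 days, and 12/180 = 6.7%. The figure of 180 comes out only with 30-day intervals (6 × 30), which is how Table 3 numbers its days.

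**2. Gap between the Table 3 day and 7 × week.**

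| Visit | 7 × week | Table 3 day | Gap |
|---|---|---|---|
| Week 4 | 28 | 30 | 2 |
| Week 12 | 84 | 90 | 6 |
| Week 24 | 168 | 180 | 12 |

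**3. What the injection window allows.** The interval is 28 − 2 = 26 to 28 + 5 = 33 days. If the window runs from one injection to the next, the last visit can fall from 6 × 26 = 156 to 6 × 33 = 198 days, which includes 180. If it is fixed to the nominal week, the range is 168 − 2 = 166 to 168 + 5 = 173 days, which does not. The plan does not say which applies.

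**4. The two time origins.** Let discharge fall L days after the first injection (L ≥ 0; no value is given). The 180-day window closes L + 180 days after injection. A last visit at 168 days leaves (L + 180) − 168 = 12 + L days uncovered, so at least 12. A last visit at 180 days still leaves L days uncovered.

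**5. Collection after the last visit.** Following a visit at 168 days, the call falls at 168 + 25 = 193 to 168 + 35 = 203 days after injection. It reaches the end of the window if L is at most 193 − 180 = 13 days for the earliest call, or 203 − 180 = 23 days for the latest. Under section 9.5.1.5, AEs are collected through the last visit, and SAEs for 30 days after the last dose or to the follow-up contact, whichever is later: 168 + 30 = 198 days or more. Inpatient hospitalization is an SAE criterion (section 9.5.1.6). An ED visit without admission need not be one.

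**6. The 30- and 90-day windows.** Counted by event date, they close at L + 30 and L + 90 days after injection. Both lie within a 168-day follow-up if L is no more than 138 and 78 days respectively. They are shortened only if the value recorded at the Week 4 or Week 12 visit is taken as the 30- or 90-day value (gaps of 2/30 and 6/90, each 6.7%, plus L). Section 9.7.4.1 leaves that possible: the primary data set for efficacy by visit is built from scheduled Phase B visits, and the observed-case set uses hospitalization/ED data recorded at each relevant time point.

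**7. Illustration of size.** Assume a constant hazard, that the 30% and 15% in section 9.7.2 are 180-day rates, and that counting stops at day 168. The observed rate is 1 − (1 − p)^(168/180):
- p = 0.30: 1 − 0.70^0.933 = 0.283, a loss of 1.7 percentage points
- p = 0.15: 1 − 0.85^0.933 = 0.141, a loss of 0.9 percentage points

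**The case against.** The strongest reply is that a visit label does not truncate anything. The endpoint is already defined in days after discharge. All episodes of care go into source documents. SAE collection and the follow-up call run past day 180 from the first injection: even with a last visit at 156 days, the earliest call is at 156 + 25 = 181. The statement "The end of the study was the date of the last study visit for the last subject" fixes the end of the trial, not a cut-off for each subject's events. Table 3 itself puts the last visit at Day 180, and 30-day intervals fit within 26 to 33 days.

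Much of this stands. A reader might infer that the last visit cannot fall on Day 180, or that observation is known to stop at day 168; the interval window and the later safety collection support neither. A reader might also infer a bias towards once-monthly treatment at all three time points. With events counted by date, the 30- and 90-day windows lie well inside follow-up, so the differences of 2 and 6 days are differences of label, not lost observation.

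What the reply does not supply is a named source for prospective events up to 180 days after discharge. The call is specified for AEs and medications, safety reporting is not designated as an endpoint source, and the claims search stops at consent. Admissions may be captured after the last visit; ED visits without admission, and events in subjects who cannot be reached or who withdraw consent, may not be.

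**Conclusion.** The week count and the stated 180 days contradict each other, and this is certain: 168 against 180. The consequence is conditional. For a subject on the nominal week schedule, with visits counted from the first injection, the last visit comes at least 12 days before the 180-day post-discharge window closes, and nothing in the plan is designated to collect endpoint events for those days. The 180-day comparisons are at risk, ED visits most of all. The designated primary comparison, at 30 days, and the 90-day comparison are affected only if events are assigned by visit label.

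The likely size is modest: 0.9 to 1.7 percentage points under the assumptions of the illustration. Section 9.7.2 gives no time frame for its rates, so these figures show scale and are not an estimate of bias. The study ended early with no statistical analysis, so no reported result is affected; the point concerns the planned methods and any reuse of the design.

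**What to change.** - Reconcile the week and day labels in section 9.1.4.2, the synopsis and Table 3, and correct the stated 180-day total so that it agrees with them. The injection schedule is left unchanged.
- State in section 9.7.1 that hospitalizations and ED visits are counted by event date, within 30, 90 and 180 calendar days after discharge, whatever the visit dates.
- Name the source: repeat the existing MO HealthNet/DMH query for the post period, so that both windows are drawn from the same data.
- Add a question on hospitalizations and ED visits to the follow-up call that is already planned. The repeated query covers cases where a late discharge puts the end of the window after the call.

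The cost is one repeated data query, one added question on an existing call, and SAP wording. No visit is added.

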#### Baseline assessments were:

- Contact from the community support worker (CSW) or study coordinator (SC) via telephone or in-person
- Routine vital signs (e.g., blood pressure, heart rate, respiratory rate, and temperature)
- Height, weight, and calculation of BMI
- Fasting lipid profile (e.g., fasting triglycerides, cholesterol [total, HDL, LDL])
- HbA1c
- Prolactin concentration
- CGI-I
- C-SSRS (Since Last Visit) for suicidality
- AIMS, BARS, and SAS to assess EPS
- PSP
- Injection site reaction assessment (i.e., localized pain, redness, swelling, and induration), if applicable
- AEs and concomitant medications
- Aripiprazole once monthly IM injection plus Day 1 of 14 days of oral aripiprazole, (last baseline procedure), unless subject received injection while hospitalized prior to study entry.

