The treating clinician performed a clinical interview and mental status examination based on current clinical standards of care at all outpatient visits, whether scheduled or unscheduled. All episodes of clinical care (i.e., psychiatric and non-psychiatric) were recorded in the source documentation. In addition, the following clinical evaluations were performed as outlined in Table 3:

- Routine vital signs (e.g., blood pressure, heart rate, respiratory rate, and temperature) at each visit
- Height, weight and calculation of BMI at each visit
- Fasting lipid tests [e.g., fasting triglycerides, cholesterol (total, HDL, LDL)]
- HbA1c
- Additional clinical laboratory testing (e.g., hematology, fasting clinical chemistry, prolactin, urinalysis and urine pregnancy test) as described in Table 3 and clinically indicated and determined by treatment team
- AEs and concomitant medications
- CGI-I
- PSP
- C-SSRS (Since Last Visit) for suicidality
- AIMS, BARS, and SAS to assess EPS
- Injection site reaction (i.e., localized pain, redness, swelling, and induration)

Final; 26 Feb 2018 Page 29 of 80

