# 9.3.1 Inclusion Criteria

Subjects must have met all of the following criteria to be included in this study:

- 1. Were able to provide written informed consent.
- 2. Were male and female subjects 18 to 65 years of age, inclusive, at time of informed consent

Final; 26 Feb 2018 Page 30 of 80

- 3. Had a current and confirmed diagnosis of schizophrenia as defined by DSM-5 criteria and a history of the illness for at least 6 months prior to screening from a reliable source (e.g., subject, family member, friend, caregiver, healthcare provider, or medical records)
- 4. Present at one of the selected inpatient units with acute psychotic symptoms for hospitalization at study entry
- 5. Had a clinically indicated need for a change in current antipsychotic therapy
- 6. Were on Medicaid with searchable claims data or were Medicaid-eligible
- 7. Had at least one inpatient psychiatric hospitalization or psychiatric ED visit within the 6 months prior to screening as confirmed through Medicaid or all available medical records and reliable data from caregivers
- 8. Had been previously prescribed oral antipsychotic treatment for at least a substantial portion of the 6 consecutive months prior to screening, with estimated duration of prescribed treatment within the 6 months prior to screening as determined by Principal Investigator discretion and confirmed through Medicaid or all available medical records and reliable data from caregivers
- 9. Had a history of response to antipsychotic treatment, with no history of clozapine treatment
- 10. Were able to understand the nature of the study and follow protocol requirements, including the prescribed dosage regimens, tablet ingestion, aripiprazole once monthly injection, and discontinuation of prohibited concomitant medications
- 11. Were able to read and understand the written word with a passing score of 4 to 6 (i.e., equivalent to seventh to eighth grade reading level for REALM-SF literacy assessment) in order to complete subject-reported outcomes measures
- 12. Were willing to accept a monthly injection
- 13. Were male and female subjects who were surgically sterile (i.e., have undergone orchiectomy or hysterectomy, respectively); female subjects who were postmenopausal for at least 12 consecutive months; or male and female subjects who agreed to use an approved form of birth control during study participation

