d: Previous medications taken within 7 days prior to starting study drug and all central nervous system-active compounds taken within 30 days preceding the first dose of study drug were recorded. All antipsychotic medications used within 6 months of screening were recorded.

e: A urine pregnancy test was performed for women of childbearing potential only at screening, Visit 10, and at the Follow-up visit; subsequent testing was done as is clinically indicated. If a subject or investigator suspected that the subject may be pregnant, a serum pregnancy test would then be performed.

**Table 3:** Schedule of Assessments

Visit				2	3	4	5	6	7	8 q
Study Period	Screening/ Assessment	Phase A (Oral Tolerability Phase a )			Pha	nse B (Trea	tment Ph	ase)		
Day	Variable	-3 to -1	Baseline Day 1 b,g	15 g	30	60	90	120	150	180
Week				2 e	4	8	12	16	20	24
Procedure										

- f: Data regarding psychiatric and non-psychiatric hospitalizations and medical interventions occurring within the 6 months prior to the date of the signing the ICF were obtained by searching MO HealthNet (Medicaid) and MO Department of Mental Health (DMH) data via collaboration with the Missouri Institute of Mental Health (MIMH); availability of Medicaid data and documentation of at least one inpatient hospitalization or ED visit within the previous 6 months was required for eligibility.
- g: For subjects who were psychiatrically stabilized and discharged prior to the completion of the required 14-day course of oral aripiprazole, a pre-discharge assignment was given to a CSW or SC. The CSW/SC maintained regular contact with the subject until the Week 2 visit. Following the Week 2 visit, subjects had contact with their assigned CSW/SC based on routine clinical care.
- h: At all outpatient visits, scheduled or unscheduled.
- i: Vital signs were recorded daily while hospitalized.
- j: BMI was calculated as: mass (kg)/height (m2).
- k: Subjects should have been fasting for a minimum of 10 hours prior to blood draws for all laboratory assessments. Every effort was made to obtain the clinical laboratory samples at the same time of day at each visit. All laboratory testing was performed at local laboratories at the clinical sites.

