## Efficacy:

- Comparison of:
  - o 30-, 90-, and 180-day rates of unscheduled psychiatric ED visits compared with prior 30-, 90-, and 180-day unscheduled visits
  - Psychiatric ED visits plus hospitalizations compared with prior 30-, 90-, and 180-day psychiatric visits plus hospitalizations
  - Total psychiatric hospitalization days over the 30-, 90- and 180-day study period compared with the total psychiatric hospitalization days over the prior 30-, 90- and 180-day period
  - o Change from baseline in CGI-I, based on the initial CGI-S, and CGI-I scores at 30-, 90-, and 180-days
- Changes from baseline on the following indicators for CMR after receiving aripiprazole once monthly:
  - Weight and BMI
  - o Fasting glucose concentrations, HbA1c concentrations, and fasting lipids concentrations (i.e., fasting triglyceride, total cholesterol, HDL, and LDL)

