## 9.7.1.9 Efficacy Analyses

The primary objective of the study was to evaluate the effect of aripiprazole once monthly on 30-, 90-, and 180-day psychiatric re-hospitalization rates following discharge due to symptoms associated with schizophrenia, compared with retrospective 30-, 90-, and 180-day psychiatric hospitalization rates in subjects previously treated with oral antipsychotic medication.

Because all primary and secondary outcome measures described in the specific aims were continuous and a reflection of a single design configuration involving longitudinal measures, in some cases including retrospective as well as prospective time points, the basic structure of the data analytic strategies was the same for all objectives.

The primary and secondary outcomes were to be analyzed using repeated measures analysis of covariance (ANCOVA) models. For example, in the three primary outcome models, testing for a main effect of time on 30-, 90-, or 180-day pre-hospitalization (i.e., oral antipsychotic) versus 30-, 90-, or 180-day post-hospitalization (i.e., aripiprazole once monthly) rates, respectively. Covariates would have included psychiatric symptoms severity at baseline, measured by CGI-S scores.

Some secondary outcome measures such as BMI, fasting lipid parameters, and glucose that were measured at time points post-hospitalization only (i.e., at baseline, 30-, 90-, and 180-days) were to be evaluated using mixed model repeated measures analysis of variance to determine whether there are changes over time. Other covariates could include race, gender, age, family history of diabetes, and BMI.

Only one primary specific objective was defined, with three time-point comparisons (i.e., 30, 90, and 180 days) with the primary comparison being hospitalization rate for the period of 30 days pre-hospitalization (i.e., at least one, based on the index hospitalization) to 30 days post-hospitalization both because of the importance of that objective and to minimize multiple comparisons concerns. Because of the multiple comparisons issue, p-values associated with the secondary and exploratory analyses performed were to be interpreted cautiously as hypothesis-generating rather than as hypothesis-confirming.

Final; 26 Feb 2018 Page 56 of 80

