AIMS = abnormal involuntary movement scale, BARS = Barnes Akathisia Rating Scale, BMI = body mass index, CGI = Clinical Global Impression, ER = emergency room, HbA1c = glycosylated hemoglobin, HDL = high-density lipoprotein, LDL = low-density lipoprotein, N/A = not applicable, SARS = Simpson-Angus Rating Scale, SD = standard deviation

Note: Standard deviations not provided for Day 150 and Day 180 data due to n = 1 subject

- a: Scale = normal, not all ill (1), borderline mentally ill (2), mildly ill (3), moderately ill (4), markedly ill (5), severely ill (6), among the most extremely ill patients (7)
- b: Scale = very much improved (1), much improved (2), minimally improved (3), no change (4), minimally worse (5), much worse (6), very much worse (7)
- c Scale = none (0), minimal, maybe extreme normal (1), mild (2), moderate (3). Severe (4)
- d: Only 1 subject had ER visits (n = 3) and psychiatric hospitalizations (n = 1)

Final; 26 Feb 2018

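### Height is read at nine time points and no single height is fixed per adult subject, so height discrepancies between visits add avoidable noise to BMI change

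*Combined protocol and SAP*

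**What the plan says.** The baseline list in Section 9.1.4.1 includes "Height, weight, and calculation of BMI", and Section 9.1.4.2 repeats it for the treatment visits: "Height, weight and calculation of BMI at each visit". In Table 3 the row "Height, weight, BMI" is marked at screening and at all eight Phase B visits (Days 1, 15, 30, 60, 90, 120, 150 and 180). The Phase A cell is blank, so there are nine time points.

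Section 9.5.1.7.2 and Table 3 footnote j define BMI as weight in kg over height in metres squared. Neither says which visit's height is used. No section gives a method, a number of readings or a tolerance for height.

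BMI is an endpoint. Section 9.7.1.2 lists weight and BMI under "Changes from baseline on the following indicators for CMR after receiving aripiprazole once monthly". Section 9.7.1.9 sends BMI to a mixed-model repeated measures analysis at baseline and Days 30, 90 and 180. The population is adult; the age criterion in Section 9.3.1 reads "Were male and female subjects 18 to 65 years of age, inclusive, at time of informed consent".

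**The concern.** Over 180 days an adult's height is effectively constant. Any difference between two height readings in the same subject is therefore measurement, conversion or entry error. Because BMI divides by height squared, that error becomes an apparent change in BMI with no change in the subject. Read literally, the plan recomputes BMI from a fresh height at every visit and so brings in this error with no gain in information.

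At stake is the precision of one secondary cardiometabolic endpoint. The primary endpoint and the sample size do not depend on BMI.

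**Working it through.** **Inputs.** Screening means from Table 5: weight 80.02 kg (SD 16.36), height 167.48 cm, BMI 29.08 kg/m². From Table 8, Day 150: 161.29 cm, 87.70 kg, BMI 33.71. Day 180: 161.20 cm, 89.30 kg, BMI 34.37. The Table 8 note says "Standard deviations not provided for Day 150 and Day 180 data due to n = 1 subject", so these two columns can be checked directly.

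**1. Reproduce the printed BMIs.**
- Day 150: 87.70 / 1.6129² = 33.71, as printed.
- Day 180, own height: 89.30 / 1.6120² = 34.37, as printed.
- Day 180, Day 150 height: 89.30 / 1.6129² = 34.33, not as printed.

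Each BMI was computed from its own visit's height.

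**2. Size of the artefact.** Assume the single subject is the same at both visits.
- Printed change: 34.37 − 33.71 = 0.66 kg/m².
- Change with height fixed at 161.29 cm: (89.30 − 87.70) / 1.6129² = 0.615, or about 0.62.
- Difference: about 0.04 kg/m², from 0.09 cm of height plus a little rounding.

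**3. Compare with 1 kg of weight.** At the mean height, 1 kg moves BMI by 1 / 1.6748² = 0.36 kg/m². The net height discrepancy that matches this is about h / (2W):
- mean weight: 167.48 / (2 × 80.02) = 1.05 cm
- one SD heavier (96.38 kg): 0.87 cm
- one SD lighter (63.66 kg): 1.32 cm
- the Day 150 subject: 161.29 / (2 × 87.70) = 0.92 cm

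The observed 0.09 cm is about a tenth of that.

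**4. Noise added to BMI change.** The documents give no height-error SD, so s = 0.5 and 1.0 cm per reading, independent between visits, is an assumption. Added SD = √2 × 2 × BMI × s / h:
- s = 0.5 cm: 1.414 × 2 × 29.08 × 0.5 / 167.48 = 0.246 kg/m²
- s = 1.0 cm: 0.491 kg/m²

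**5. Loss of effective sample size.** With added SD a and true SD of BMI change d (also an assumption), the loss is a² / (d² + a²).

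| True SD d (kg/m²) | s = 0.5 cm | s = 1.0 cm |
|---|---|---|
| 0.5 | 19% | 49% |
| 1.0 | 6% | 19% |
| 2.0 | 1.5% | 6% |

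**6. Group means.** Mean height in Table 8 is 167.03, 166.76 and 166.96 cm at Days 15, 30 and 60. Table 8 prints no n for these visits. The CGI-I means and SDs there fit n = 5 and no other n from 2 to 8. If the same five subjects were measured each time (assumption), summed height moved by 5 × (166.76 − 167.03) = −1.35 cm and then by 5 × (166.96 − 166.76) = +1.00 cm. This cannot be assigned to individuals.

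**The case against.** The strongest reply is that the evidence for a material error is thin. The only discrepancy visible in one subject is 0.09 cm. Since 161.29 cm is exactly 63.5 inches (63.5 × 2.54), the pair may reflect unit conversion or data entry rather than a second measurement. Mean height is identical at Days 90 and 120, at 171.82 cm (SD 13.82), so movement does not appear at every visit. Weight change is a separate secondary endpoint with no height error, and in adults it carries almost all the information in BMI change. Section 9.7.1.9 already treats secondary p-values as hypothesis-generating, and Section 9.7 states that no formal analysis was performed.

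All of this stands, and it limits the importance of the point. It does not remove it: one stored height per subject prevents measurement, conversion and entry discrepancies alike, and nothing in the documents gives a reason for repeating adult height.

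A reader might infer more than the documents support:
- **That height error in this trial outweighed a 1 kg weight change.** It could do so, but only with a net discrepancy of about 1.05 cm at the mean subject. No individual discrepancy of that size is shown.
- **That a particular share of the sample size was lost.** Both SDs behind that figure are assumed, and the result runs from 1.5% to 49%.
- **That BMI and weight moved in opposite directions.** In Table 8 mean BMI and mean weight move the same way at every consecutive step from screening to Day 180.

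**Conclusion.** The point holds as a minor one. The plan requires nine heights per adult and no rule fixes one of them for BMI, and the n = 1 columns show that visit-specific heights reached the reported BMI. The demonstrated effect is about 0.04 kg/m² on a reported change of 0.66, if the same subject is in both columns. The larger figures, an added SD of about 0.25 to 0.49 kg/m² and the sample-size losses tabulated above, rest on assumed error and true-change SDs and show only a plausible range. The effect is extra noise rather than bias, provided height is read the same way throughout. Weight change is untouched.

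**What to change.** State in Section 9.5.1.7.2 and Table 3 footnote j that every BMI is computed from one height per subject, taken at screening (or at baseline). Remove height from the later visits in Sections 9.1.4.1 and 9.1.4.2 and in Table 3, keeping weight at each visit. If baseline is the chosen reading, it stays in Section 9.1.4.1. Duplicate readings at the chosen visit are optional. Existing BMI values can be recomputed in the same way from the subject-level data.

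The cost is a minor wording change, made through the written amendment or administrative change that Section 13.1 requires. It needs no extra subjects and takes a procedure out of the later visits.
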